**Table 1. Suspected liver injury cases according to drug induced liver injury (DILI) criteria**

Baseline Value of ALT/AST	Criteria to discontinue investigational product
>ULN and <2× ULN	ALT or AST >5× baseline value
≥2× ULN but <5× ULN	ALT or AST >3× baseline value
≥5× ULN	ALT or AST >2× baseline value
>ULN	ALT or AST >2× baseline value and (BILI >2× ULN OR INR >0.2)
Within Normal Range	ALT or AST >8× ULN
	ALT or AST >5× ULN
	ALT or AST >3× ULN and (BILI >2× ULN or INR >1.5)

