## 6.8.1. Monitoring and Discontinuation for Suspected Drug-induced Liver Injury (DILI) Criteria

A subject will be additionally monitored if they meet any of the following liver-related criteria. Baseline value is defined as the last ALT and AST values performed prior to or on the

New transaminase elevations in subjects with baseline value within the normal range:

For new elevations in transaminases greater than 2× ULN, repeat measurement should be performed within 48 to 72 hours. If elevations persist, subjects should be evaluated for other causes of transaminase elevations and with tests of hepatic function. If no other cause is identified, then the subjects need to be monitored closely (see below), and discontinuation of the study drug should be considered.

Drug should be discontinued, and the subject followed until resolution of symptoms or signs in the following situations:

- ALT or AST >8× ULN
- ALT or AST >5× ULN for more than 2 weeks
- ALT or AST  $>3 \times$  ULN and (TB  $>2 \times$  ULN or INR >1.5)
- ALT or AST >3× ULN with the appearance of fatigue, nausea, vomiting, right upper quadrant pain or tenderness, fever, rash, and/or eosinophilia (>5%)

New transaminase elevations in subjects with baseline ALT or AST > ULN:

For new elevations in transaminases greater than 2× baseline value or total bilirubin >1.5× ULN, repeat measurement should be performed within 48 to72 hours. If elevations persist, subjects should be evaluated for other causes of transaminase elevations and with tests of hepatic function. If no other cause is identified, then the subjects need to be monitored closely (see below), and discontinuation of the study drug should be considered.

Drug should be discontinued and the subject followed until resolution of symptoms or signs in the following situations described in Table 3:

Table 3: Discontinuation Criteria in Subjects with Abnormal Baseline ALT or AST Values

| Baseline value of ALT/AST | Criteria to discontinue investigational product  |
|---------------------------|--|
| <2× ULN                   | if ALT or AST increases to >5× baseline value  |
| ≥2× ULN but <5× ULN       | if ALT or AST increases to >3× baseline value  |
| ≥5× ULN                   | if ALT or AST increases to >2× baseline value  |

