| Other                     | if ALT or AST increase >2× baseline value AND the increase is accompanied by a concomitant total bilirubin increase to >2× ULN OR the INR concomitantly increases by >0.2                          |
|                           | if ALT or AST increase >2× baseline value in the presence of signs and symptom(s) such as fatigue, nausea, vomiting, right upper quadrant pain or tenderness, fever, rash, and/or eosinophil (>5%) |

ALT = alanine aminotransferase; AST = aspartate aminotransferase; INR = International Normalized ratio; ULN = Upper limit of normal

Close monitoring for suspected DILI includes:

- Repeating liver enzyme and serum bilirubin tests 2 or 3 times weekly. Frequency of repeat testing can decrease to once a week or less if abnormalities stabilize or the trial drug has been discontinued and the subject is asymptomatic.
- Obtaining a more detailed history of symptoms and prior or concurrent diseases.
- Obtaining a history of concomitant drug use (including non-prescription medications and herbal and dietary supplement preparations), alcohol use, recreational drug use, and special diets.
- Ruling out acute viral hepatitis types A, B, C, D, and E, autoimmune or alcoholic hepatitis, hypoxic/ischemic hepatopathy; and biliary tract disease.
- Obtaining a history of exposure to environmental chemical agents.
- Obtaining additional tests to evaluate liver function, as appropriate (e.g., INR, direct bilirubin).
- Considering gastroenterology or hepatology consultations.

Note: If a subject lives in a remote area, laboratory testing can be performed locally, and the results should be promptly communicated to the Investigator site.

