## 1 INTRODUCTION

The purpose of this statistical analysis plan (SAP) is to describe the statistical methods, data derivations and data summaries that will be used to analyze and report results for Protocol BIO89-100-221 Version 3.0.

The SAP will supersede the protocol in the event of any differences between the two documents in the plans for data analysis, and the protocol will be amended if appropriate. The SAP will be included as an appendix in the clinical study report.

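### SAP Table 1 turns two protocol liver stopping criteria into looser ones: an absolute INR above 0.2 instead of a rise above 0.2, and above 5× ULN without the two-week duration

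*SAP*

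**What the plan says.** SAP 4.4.2 plans a summary of suspected liver injury cases using the criteria in SAP Table 1. The right-hand column of that table is headed as the criteria for stopping investigational product. Two of its rows differ from protocol 6.8.1.

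- **Baseline ALT or AST above ULN.** The SAP row is "ALT or AST >2× baseline value and (BILI >2× ULN OR INR >0.2"). The matching entry in protocol Table 3 has the same transaminase and bilirubin parts, but its INR part is that "the INR concomitantly increases by >0.2".
- **Baseline within normal range.** The protocol criterion is "ALT or AST >5× ULN for more than 2 weeks". The SAP row keeps the 5× ULN threshold and gives no duration.

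For abnormal baselines, the protocol treats a doubling alone as a reason to retest: "For new elevations in transaminases greater than 2× baseline value or total bilirubin >1.5× ULN, repeat measurement should be performed". If the rise persists and no other cause is found, "discontinuation of the study drug should be considered".

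SAP section 1 settles precedence: "The SAP will supersede the protocol in the event of any differences between the two documents in the plans for data analysis". No readable SAP text restores the INR change or the duration. The table shells are a separate document and the sample code in SAP Appendix 2 is redacted, so the programming cannot be checked.

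**The concern.** The table is presented as a count of subjects who met the protocol's liver stopping criteria. If two of its rows are looser than the protocol, it will name subjects as meeting a stopping criterion when the protocol asked only for a repeat test or closer monitoring. Because the SAP takes precedence for data analysis, a programmer cannot simply fall back on the protocol wording. The effect of BIO89-100 on liver function biomarkers is a stated safety objective, so a reader of the study report would take the count at face value.

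**Working it through.** No power or sample-size figure is involved. The check sets the two rules side by side and works out which subjects they classify differently.

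**INR row (baseline above ULN)**

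Let *b* be baseline and *p* peak ALT or AST in multiples of ULN, and *r* = *p*/*b*.

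- Protocol: *r* > 2 and (bilirubin > 2× ULN or INR rise > 0.2)
- SAP: *r* > 2 and (bilirubin > 2× ULN or INR > 0.2)

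With an INR result, the last SAP condition is always true, so the rule collapses to *r* > 2. With no INR result, the SAP row works correctly through bilirubin.

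Example: *b* = 1.5, *p* = 3.3 (so *r* = 2.2), bilirubin 0.6× ULN. The INR values are assumed.

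| INR, baseline to post-baseline | Protocol row | SAP row |
|---|---|---|
| 0.9 to 0.9 | no | yes |
| 1.0 to 1.0 | no | yes |
| 1.0 to 1.1 | no | yes |
| 1.0 to 1.2 | no | yes |
| 1.0 to 1.3 | yes | yes |
| 1.1 to 1.5 | yes | yes |

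A subject may be listed wrongly in this row and still belong in the table through another row. The subjects who meet no protocol criterion at all are those with *r* above 2 and up to the protocol's transaminase-only tier, given unchanged bilirubin and INR, an INR result, and no listed symptom or eosinophilia. That tier is 5× baseline for *b* < 2, 3× for 2 ≤ *b* < 5, and 2× for *b* ≥ 5.

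| *b* (× ULN) | Above 2*b* | Up to tier × *b* |
|---|---|---|
| 1.2 | 2.4 | 5 × 1.2 = 6.0 |
| 1.5 | 3.0 | 5 × 1.5 = 7.5 |
| 2.5 | 5.0 | 3 × 2.5 = 7.5 |
| 3.0 | 6.0 | 3 × 3.0 = 9.0 |
| 5.0 | 10.0 | 2 × 5.0 = 10.0 (empty) |

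Without an INR result the band is empty at every baseline. With one, the 5× and 3× baseline tiers add nobody to the table, because both lie inside *r* > 2.

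**5× ULN row (normal baseline)**

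| Peak, duration | Protocol 5× row | SAP 5× row | 8× row (both documents) |
|---|---|---|---|
| 5.5× ULN, 3 days | no | yes | no |
| 5.5× ULN, 14 days | no | yes | no |
| 5.5× ULN, 15 days | yes | yes | no |
| 8.5× ULN, 3 days | no | yes | yes |

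The subjects meeting no protocol criterion are those with peaks above 5 and up to 8× ULN lasting two weeks or less, again with unchanged bilirubin and INR and no symptom or eosinophilia. Since > 8 implies > 5, the 8× row adds no further subject.

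**The opposite direction**

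SAP Table 1 also omits the protocol's symptom and eosinophilia criteria. For normal baselines that criterion is "ALT or AST >3× ULN with the appearance of fatigue, nausea, vomiting, right upper quadrant pain or tenderness, fever, rash, and/or eosinophilia (>5"%). For abnormal baselines it is a rise above 2× baseline with a similar list ending "right upper quadrant pain or tenderness, fever, rash, and/or eosinophil (>5"%). Taking eosinophils at 6% and normal bilirubin:

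| Subject | Protocol | SAP as written | SAP with only the INR wording corrected |
|---|---|---|---|
| *b* = 1.5, *r* = 2.5, no INR result | yes | no | no |
| *b* = 1.5, *r* = 2.5, normal unchanged INR | yes | yes | no |
| Normal baseline, 4× ULN, normal INR | yes | no | no |

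The middle subject is caught today only by accident, and would leave the table if the INR wording alone were corrected.

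**The case against.** The strongest reply on INR is that nobody would set an absolute cut-off of 0.2, so the entry must be shorthand for an increase; SAP 4.4.2 already plans changes from baseline for safety laboratories. That is plausible. But the same table uses INR > 1.5 as an absolute value in the normal-baseline group, and nothing tells the programmer to read the two entries differently.

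On duration, scheduled on-treatment chemistry is sparse, so persistence beyond two weeks often cannot be derived, and flagging any value above 5× ULN is a cautious screen. This has force, and the omission may be deliberate. It does not justify showing the row under a heading that calls it a stopping criterion.

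Three narrower points stand. Nested thresholds shown row by row remain informative, so the redundancy of the higher tiers is a consequence rather than a separate fault. Protocol exclusion 7 bars ALT or AST above 3× ULN at screening, so baselines above that need a later pre-dose rise; the worked case at 5.0× ULN is close to hypothetical. The INR effect also needs an INR result, and the coagulation visits are redacted.

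Finally, the consequence is small. Treatment is stopped under protocol 6.8.1, and laboratory shifts and listings allow a flagged case to be checked. This limits the weight of the point but does not remove the error.

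**Conclusion.** The point holds as a minor one. Both SAP rows are complete as printed, differ from the protocol, and are not explained by redaction or a broken table. Each row can only add cases relative to its protocol counterpart.

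The net direction for the whole table is not established, because the missing symptom and eosinophilia criteria remove cases. The documents give no liver-event rate and do not show when INR is measured, so the number of subjects affected cannot be estimated. The INR conclusion assumes only that the recorded INR exceeds 0.2 and has not risen by more than 0.2. The effect is confined to one descriptive safety table.

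**What to change.** - Rewrite the INR row as *ALT or AST > 2× baseline and (bilirubin > 2× ULN or INR increase from baseline > 0.2)*.
- Restore the more-than-two-weeks condition on the > 5× ULN row. Where persistence cannot be derived, label the entry a single-value elevation, not a stopping criterion.
- Add a footnote that the protocol's symptom and eosinophilia (> 5%) criteria are not tabulated. Without it, correcting the INR row would silently drop subjects who do meet the protocol.

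The cost is a few words of SAP text, one footnote and one derived variable, the INR change from baseline. SAP 5.1 can supply that baseline: its exception for liver tests does not appear to cover INR, which SAP 7.6.2 places in the coagulation panel. Data collection does not change.

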## 5 DEFINITIONS

### 5.1 BASELINE DEFINITION

In general, baseline will be defined as the most recent non-missing measurement (scheduled or unscheduled) prior to the administration of the first dose of IP. For numerical measurements that have duplicates or triplicates (for the same visit), the arithmetic mean will be used. Some measurements have special definitions of baseline, which are defined below.

The mean TG value will be used for stratification factor [REDACTED]

Baseline Triglyceride is defined as the average of [REDACTED] and the preceding two lipid-qualifying visits collected in EDC. Fasting status is required for the TG values to be included.

The definition of baseline of other lipid panel labs is the average of last two non-missing screening fasting values and [REDACTED] value (Pre-dose, fasting).

The definition of baseline vital signs is the average of the last two non-missing screening values and [REDACTED]. If there is Case Report Form (CRF) average value on duplicate measurements of BP and/or Pulse on [REDACTED], only the individual values will be included in the baseline derivation.

The baseline definition for MRI for subjects of the main cohort is the [REDACTED] value. The baseline definition for MRI for subjects of the fibrate expansion cohort is the value obtained between [REDACTED]

The baseline definition for safety numeric measurements (except for liver tests) is the average of last two non-missing screening values and [REDACTED]

The baseline definition of PK is the [REDACTED]. The details will be described in a

separate document.

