### 7.6.2 Clinical Laboratory Parameters

The following laboratory assessments will be analyzed using the safety analysis set:

**Hematology:** White Blood Cell (WBC) with differential (Total Neutrophils, Lymphocytes, Monocytes, Eosinophils, Basophils – absolute and %), Red blood cell (RBC) count, RBC Indices (Mean Corpuscular Volume [MCV], Mean Corpuscular Hemoglobin Concentration [MCH], Mean Corpuscular Hemoglobin Concentration [MCHC], Red Cell Distribution Width [RDW], Reticulocyte count) Hemoglobin, Hematocrit, Platelet count, Coagulation panel (including Prothrombin Time, International Normalized Ratio (INR), Activated Partial Thromboplastin Time [aPTT])

**Lipid Assessment:** [REDACTED], ApoB, [REDACTED] non-HDL-C, LDL-C, [REDACTED]  
[REDACTED], TG, VLDL-C, VLDL-TG.

**Clinical Chemistries:** Alkaline Phosphatase (ALP), ALT, AST, Albumin, Bicarbonate, BUN (Blood urea nitrogen), Calcium, Creatinine, eGFR, Creatine Kinase (CK), Chloride, Fasting plasma glucose, Gamma-Glutamyl Transferase (GGT), Lactate dehydrogenase, Magnesium, Phosphorus, Potassium, Sodium, (Total bilirubin, Indirect/direct bilirubin), Total protein, Uric acid. For ALT, change and percent change from baseline at week 8 will be analyzed using MMRM method based on full analysis set.

**Urinalysis:** Basic urinalysis (dipstick, including macroscopic appearance, bilirubin, blood, color, glucose, ketones, leukocyte esterase, nitrite, pH, protein, specific gravity, urobilinogen); Full urinalysis (dipstick plus microscopic evaluation) to be performed only at the screening and End of Study visits). A reflex microscopic urinalysis should be performed if the results of the urinalysis is abnormal or at the discretion of the Principal Investigator (PI) or delegate. A listing will be presented for Urinalysis results.

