PK = pharmacokinetics; PT = prothrombin time; RNA = ribonucleic acid; RR = respiratory rate; RLP-C = remnant lipoprotein-cholesterol; SAE = serious adverse event; SoA = Schedule of Assessments; T3 = triiodothyronine; T4 = thyroxine; [REDACTED]; TG = triglyceride; TSH = thyroid-stimulating hormone; V = Visit; VLDL-C = very low-density lipoprotein cholesterol; VLDL-TG = very low-density lipoprotein triglycerides; WBC = white blood cell; WOCBP = women of childbearing potential.

Body posture during TG, BP, heart rate, RR and body temperature measurement needs to be the same (e.g., sitting, semi-erect, or supine) throughout the study with resting for at least 5 min prior to measurement at each study visit.

Fasting blood samples should be taken after at least 12 hours of fasting. (It is recommended that subjects fast no more than 14 hours.) Fasting includes food and all beverages except for non-mineral water.

Hematology: Hemoglobin, hematocrit, RBC count, reticulocyte count, MCV, MCH, MCHC, platelet count, WBC count, total neutrophils, eosinophils, monocytes, basophils, lymphocytes.

Blood chemistry: BUN, creatinine (eGFR using CKD-EPI equation), fasting plasma glucose, calcium, sodium, potassium, chloride, total CO2 (bicarbonate), AST (SGOT), ALT (SGPT), ALP, GGT, total bilirubin, direct (conjugated) bilirubin, indirect (unconjugated) bilirubin, CK, uric acid, albumin, total protein. Coagulation panel: INR, aPTT, PT.

Urinalysis: pH, glucose, protein, blood, ketones, nitrites, leukocyte esterase, urobilinogen, urine bilirubin, microscopy.

a = If [REDACTED] is required, only assessment at that visit is TG measurement.

b = [REDACTED]

c = Symptom-driven physical assessment for applicable reported AEs. Can be conducted on site during a scheduled or unscheduled visit or by a home health provider (HHP) if identified on the delegation log. d = Height at screening [REDACTED] only.

e = Starting from randomization, pre-dose BP and pulse will be measured in duplicate. The first measurement will be initiated before dosing with sitting/semi-erect or supine position and resting for at least 5 minutes prior to measurements. BP and pulse are to be repeated at least 1 minute apart. Additional vital signs measurements may be done if clinically indicated.

f = Coagulation panel will be done at [REDACTED] only.

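### SAP Table 1 turns the protocol's INR rise of more than 0.2 into an absolute INR above 0.2, which every INR result meets

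*SAP*

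**What the plan says.** SAP 4.4.2 plans a summary of suspected liver injury cases using the criteria in SAP Table 1. For subjects with baseline ALT or AST above ULN, the combined row reads "ALT or AST >2× baseline value and (BILI >2× ULN OR INR >0.2". No footnote defines 0.2 as a change, and nothing in the row is redacted.

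The corresponding protocol rule is the row labelled Other in Table 3 (Section 6.8.1). There the rise above 2× baseline must be "accompanied by a concomitant total bilirubin increase to >2× ULN OR the INR concomitantly increases by >0.2".

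The SAP's combined row for subjects with normal baseline values uses INR above 1.5, which is a level. It agrees with protocol 6.8.1 and is not in question here.

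SAP Section 1 settles which text governs: "The SAP will supersede the protocol in the event of any differences between the two documents in the plans for data analysis".

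On baselines, protocol 6.8.1 covers the enzymes only: "Baseline value is defined as the last ALT and AST values performed prior to or on the" (the rest is redacted). SAP 5.1 says: "The baseline definition for safety numeric measurements (except for liver tests) is the average of last two non-missing screening values and" a further value that is redacted.

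**The concern.** The combined row should pick out subjects in whom an enzyme rise comes with evidence that the liver is working less well. That second condition justifies an enzyme threshold lower than those in the enzyme-only rows. If the INR part is always true, the second condition disappears for anyone with an INR result. The row then becomes an enzyme-only rule set lower than the other enzyme-only rows.

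A reader of the safety summary would see combined cases that are not combined cases, possibly in any arm including placebo, and could not separate the more serious ones. The stratum can be populated: exclusion criterion 7 removes only ALT or AST above 3× ULN at screening, so subjects between ULN and 3× ULN may enter.

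**Working it through.** The plan gives no calculated figure to reproduce, because the point is a logical criterion. The inputs are the two rules.

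**1. The rules as conditions.** Let R be ALT or AST divided by its baseline; B and B0 be on-study and baseline bilirubin in multiples of ULN; I and I0 be on-study and baseline INR.

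- Protocol Table 3: R > 2 and [(B > 2 and B > B0) or (I − I0 > 0.2)], at the same time.
- SAP Table 1: R > 2 and [B > 2 or I > 0.2].

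**2. The four cells.** Take a subject with R > 2 and an INR result.

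| Bilirubin increase to above 2× ULN | INR increase above 0.2 | Protocol | SAP |
|---|---|---|---|
| yes | yes | counted | counted |
| yes | no | counted | counted |
| no | yes | counted | counted |
| no | no | not counted | counted |

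The rules differ in the last cell. Example: ALT 2.5× baseline, bilirubin 0.6× ULN throughout, INR 1.0 at baseline and on study. The protocol does not count this subject (I − I0 = 0). The SAP does (1.0 > 0.2).

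**3. A grid check.** The documents give no INR normal range, so the values are assumed: baseline INR 0.8, 0.9, 1.0, 1.1, 1.2; on-study INR 0.8, 0.9, 1.0, 1.1, 1.2, 1.3, 1.5, 1.8; baseline bilirubin 0.5 or 1.0× ULN; on-study bilirubin 0.5, 1.0, 1.5 or 2.5× ULN; R = 2.1, 3, 4 or 6.

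- Combinations per R: 2 × 4 × 5 × 8 = 320; in total 4 × 320 = 1,280.
- SAP rule: all 1,280 count.
- Protocol rule, per R: on-study bilirubin 2.5 gives 2 × 40 = 80. The other 2 × 3 = 6 bilirubin pairs each have 5 + 4 + 3 + 2 + 2 = 16 INR pairs rising by more than 0.2, giving 6 × 16 = 96. Total (80 + 96) × 4 = 704.

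These are grid cells, not expected patients.

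**4. Overlap with the enzyme-only rows.** Those rows need R > 5 (baseline above ULN and below 2× ULN), R > 3 (2× to below 5× ULN) or R > 2 (5× ULN or more). Each implies R > 2, so every such subject with an INR result also falls in the combined row. Enzyme level needed for entry:

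- Baseline 1.5× ULN: above 2 × 1.5 = 3.0× ULN, against 5 × 1.5 = 7.5× ULN in the enzyme-only row (1 − 2/5 = 60% lower).
- Baseline 2.5× ULN: above 2 × 2.5 = 5.0× ULN, against 3 × 2.5 = 7.5× ULN (1 − 2/3 = 33% lower).

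**5. The bilirubin term.** Exclusion criterion 8 bars bilirubin above ULN except in documented Gilbert's syndrome, up to 3 mg/dL. Such a subject can exceed 2× ULN with no rise only if 2 × ULN < 3, that is ULN < 1.5 mg/dL. The documents do not give the ULN. At an assumed ULN of 1.0 the range is 2.0 to 3.0 mg/dL; at 1.4 it is 2.8 to 3.0; at 1.5 it is empty. Correcting bilirubin alone changes no count where an INR exists, since the bracket stays true. Correcting INR alone leaves these subjects counted.

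**6. Why the baseline needs stating.** Suppose pre-dose INRs are 1.0, 1.1 and 1.2 (illustrative) and the on-study value is 1.35. Against the mean of 1.1 the rise is 0.25 and counts; against the last value of 1.2 it is 0.15 and does not.

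**The case against.** The best counter-argument is that this is a transcription slip. The SAP column keeps the protocol's heading about criteria for stopping treatment, so it evidently condenses that rule. An INR cut of 0.2 is odd enough that a programmer might query it. The table shells are a separate document and the SAS code is redacted, so nobody can show that an output would be wrong. That limits the claim to the SAP text. It does not rescue the text: the other INR entry in the same table is a level, SAP 4.4.2 bases safety laboratory evaluation on observed values, and the SAP overrides the protocol on analysis.

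Second, the error acts only where an INR is available. The schedule footnote restricts the panel ("Coagulation panel will be done at" redacted visits), and close monitoring lists INR only as an example: "Obtaining additional tests to evaluate liver function, as appropriate (e.g., INR, direct bilirubin". It also starts only if the elevation persists with no other cause found. This stands: how often an INR would accompany an enzyme rise cannot be judged from the documents.

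Third, the protocol's combined row is itself set at 2× baseline, so the 60% and 33% gaps exist by design. That is right. What the SAP wording removes is the second condition that justified the lower level.

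Fourth, the baseline can be read from SAP 5.1. INR sits in the hematology list under "Coagulation panel (including Prothrombin Time, International Normalized Ratio (INR), Activated Partial Thromboplastin Time [aPTT", and the liver tests named in 4.4.2 include neither INR nor bilirubin, so averaging would apply literally. That reading is fair, but it gives these two tests a different kind of baseline from the protocol's ALT/AST baseline. With a single pre-dose INR the choice makes no difference. This is a side point, as is bilirubin.

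**Conclusion.** The concern holds. Followed as written, the SAP row counts every subject with an abnormal baseline, an INR result and ALT or AST above 2× baseline, whatever the bilirubin and INR show. The protocol requires one of two signs of impaired function. The excess is one cell of four: neither sign present.

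The conclusion assumes that an INR is available with the enzyme value and that no INR falls to 0.2 or below. Without an INR, bilirubin alone decides and the INR error has no effect. The bilirubin wording is a minor second error, confined to documented Gilbert's syndrome and to a ULN below 1.5 mg/dL. The documents do not support an expected number of miscounted subjects.

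Importance is low. One planned safety summary is affected, the protocol's stopping rule is correctly worded, laboratory values and shifts are reported separately, and no efficacy result changes. Correction is desirable rather than essential.

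**What to change.** 1. Reword the combined row for baselines above ULN, correcting both terms together: ALT or AST above 2× baseline and, concomitantly, either total bilirubin risen from baseline to above 2× ULN or INR more than 0.2 above its baseline.
2. Add one sentence naming the baseline for bilirubin and INR in this table. If the last pre-dose value is chosen to match the protocol's ALT/AST baseline, state it as an exception to the averaging rule in SAP 5.1.
3. Leave the combined row for normal baselines as it is. A flag for subjects with documented Gilbert's syndrome is optional.
4. Check the table shell and program against protocol Table 3.

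The cost is one table row and one sentence, using data already collected. No protocol amendment is needed, because the change restores the protocol rule. Two limits remain: an increase depends on the baseline chosen, and where no INR accompanies the enzyme rise the row still rests on bilirubin alone.
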